## 9.2 Exploratory Efficacy Variables

The analysis of the exploratory efficacy variable will be conducted for the FAS.

Days with seizures per 28 days for each seizure type and study period will be calculated as described for the generalized seizures in Section 8.1.2. The days with any generalized seizures

per 28 days will only be derived for subjects who completed or discontinued during the respective study period. For subjects who discontinued during the Titration period, the missing value of the maintenance period will be implemented as described in Section 4.2

Descriptive statistics will be used to summarize the proportion of subjects who have at least a 50 percent reduction in generalized seizures per 28 days by study period (Titration and Maintenance Period) and syndrome subgroup.

Descriptive statistics will also be produced to summarize the proportion of subjects who have more than 30% and 50% increase in generalized seizures per 28 days during the study period (Titration and Maintenance Period) by syndrome subgroup.

Descriptive statistics will be produced to summarize the percent change in days with any generalized seizures per 28 days during the study period by syndrome subgroup.

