The study will begin with subject screening at Visit 1 and will consist of a 6-week prospective Baseline Period where seizure frequency will be captured. Subjects/caregivers will maintain a diary to record daily seizure activity from Visit 1 until the end of the study. The subject diary will capture seizure type and seizure frequency information. If all inclusion criteria are met and no exclusion criterion is met, the subject will begin a 6-week Titration Period (LCM dosing flexibility allowed based on tolerability) starting at Visit 2. Subjects will be asked to return to the clinic on the morning of the day prior to Visit 2 to begin 24-hour ambulatory EEG recordings. Subjects will initiate treatment with LCM oral solution at 2mg/kg/day, or LCM tablets at 100mg/day based on body weight. The dose will be titrated to a level to optimize tolerability and seizure control, not to exceed 12mg/kg/day (oral solution) for subjects weighing < 50 kg, or 600mg/day (tablets/oral solution) in subjects weighing ≥ 50 kg. Subjects will increase the LCM dose in a stepwise fashion on a weekly basis to optimize tolerability and seizure control (see Figure 5-1 and Figure 5-2).

Lacosamide doses will be titrated according to the schedules presented in Table 7-1 and Table 7-2.

At the end of the Titration Period (Visit 6), a 12-week Maintenance Period will begin. The LCM dose will remain stable throughout the Maintenance Period. Subjects who require a change in dose during the Maintenance Period will be withdrawn from the study. Subjects who require a change in formulation during the Maintenance Period should consult the medical monitor to assess if the subject can continue in the study.

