5.4 Rationale for study design and selection of dose

Epilepsy is a condition for which an improved benefit/risk ratio for medicinal products remains a challenge; this is especially true for pediatric patients. Based on the demonstrated efficacy and safety of LCM as adjunctive treatment in adult subjects with partial-onset seizures, and the experience with other AEDs in pediatric subjects, it is expected that LCM will also exhibit an acceptable benefit/risk profile in the pediatric population with uncontrolled generalized seizures.

In this study, the safety and tolerability of LCM will be studied when added to 1 to 3 concomitant AEDs in pediatric subjects with epilepsy syndromes associated with generalized seizures. The study will also obtain preliminary efficacy data of LCM on seizure frequency in pediatric epilepsy syndromes associated with generalized seizures.

This study is an exploratory study to investigate on which syndromes LCM has a beneficial effect in order to plan confirmatory study(ies) and exclude syndromes for which LCM has no clear benefit or possibly induces exacerbations.

Based on the currently available LCM pediatric safety and PK data from SP847 and SP1047, as well as on information available in the medical literature, the dosing recommendations for SP0966 are as follows:

- Lacosamide dosing should aim to achieve LCM plasma concentrations equivalent to the average steady-state LCM plasma concentration reached after a LCM 200 to 600mg/day dose administration in adult studies.
- A weight-based flexible dosing scheme is recommended:
 - Subjects <50kg: LCM 4-12mg/kg/day (oral solution)
 - Subjects ≥50kg: LCM 200 to 600mg/day (tablets/oral solution)

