#### **2.2.2.2 Exploratory efficacy variables**

- At least 50 percent reduction in generalized seizures per 28 days by study period (titration and maintenance period) and syndrome subgroup
- Increase in generalized seizures of more than 25 percent per 28 days during the study period by syndrome subgroup
- Percent change in days with any generalized seizures per 28 days during the study period by syndrome subgroup

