### 8.1.2 Generalized seizures

Days with any generalized seizures per 28 days (GSD/28d) will be based on the seizure diary and will be derived separately for the Baseline Period, the Titration Period, and the Maintenance Period. Basis for the calculation will be the number of days with at least 1 generalized seizure (GSD) (absence, myoclonic, clonic, tonic, tonic clonic, atonic, partial evolving to secondarily generalized) during the considered study period and the number of days in the considered study period for which seizure information was provided (D):

$$\text{GSD/28d} = \text{GSD} \times (28/\text{D})$$

The days with any generalized seizures per 28 days will only be derived for subjects who completed or discontinued during the respective study period. For subjects who discontinued during the Titration Period, the missing value of the Maintenance Period will be imputed as described in Section 4.2.

Descriptive statistics will be provided for actual values and changes from Baseline for days with any generalized seizures per 28 days by study period. This summary will be repeated by syndrome subgroups (as described in Section 4.8).

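### SAP 2.2.2.2 and 9.2 give different cut-offs for seizure worsening and do not name the metric; if it is seizure days, children with seizures on most Baseline days cannot reach the cut-offs

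*SAP*

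**What the plan says.** SAP Section 2.2.2.2 lists the worsening variable as "Increase in generalized seizures of more than 25 percent per 28 days during the study period by syndrome subgroup". The matching analysis in SAP Section 9.2 is the "proportion of subjects who have more than 30% and 50% increase in generalized seizures per 28 days", by syndrome subgroup.

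For the metric, Section 9.2 opens with "Days with seizures per 28 days for each seizure type and study period will be calculated as described for the generalized seizures" and points to Section 8.1.2. That section says "Days with any generalized seizures per 28 days (GSD/28d) will be based on the seizure diary". Its formula is GSD/28d = GSD × (28/D), where GSD is the number of days with one or more generalized seizures and D is the number of days with diary information. In both 2.2.2.2 and 9.2, the responder and worsening items refer to seizures per 28 days. The percent-change item in each section refers to days with seizures.

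Protocol Section 5.1 says of data collection: "The subject diary will capture seizure type and seizure frequency information".

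**The concern.** The two SAP sections disagree on what counts as worsening. SAP Amendment 1 introduced both, so neither supersedes the other. The study is open-label, so a cut-off left unsettled could be chosen after results are visible.

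The metric matters because of what the study is for. Protocol Section 5.4 says one purpose is to "exclude syndromes for which LCM has no clear benefit or possibly induces exacerbations". The by-syndrome worsening proportion is the SAP's most direct summary of that question. A rate of seizure days has a ceiling, and a child near the ceiling at Baseline has little or no room to be recorded as worse. SAP Section 4.8 allows a syndrome subgroup to be shown with as few as 4 subjects. One child who cannot be counted then moves the proportion by up to 1/4, or 25 percentage points.

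**Working it through.** The plan states no figure to reproduce: it gives no ceiling, and Protocol Section 13.8 reports no formal sample size calculation. The check has two parts.

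**Cut-offs side by side.** Section 2.2.2.2 has more than 25%. Section 9.2 has more than 30% and more than 50%. A child whose rate rises by 27% meets the listed variable and appears in neither planned summary.

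**Ceiling, if the metric is seizure days.**

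Inputs:
- Rate: GSD × 28/D (SAP 8.1.2).
- Period lengths: 6-week Baseline = 42 days and 12-week Maintenance Period = 84 days (Protocol 5.1). Complete diaries are assumed.

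GSD cannot exceed D, so the rate cannot exceed 28. For a Baseline rate b, the largest possible increase is (28 − b)/b. An increase of more than t is therefore impossible when b ≥ 28/(1 + t).

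| Cut-off | Limit on b | Share of Baseline days | First blocked whole number of 42 days |
|---|---|---|---|
| >25% | 28/1.25 = 22.40 | 80.0% | 34 |
| >30% | 28/1.30 = 21.54 | 76.9% | 33 |
| >50% | 28/1.50 = 18.67 | 66.7% | 28 |

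With 40 to 44 diary days at Baseline, the first blocked numbers are 32 to 36, 31 to 34 and 27 to 30 respectively.

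Just below each limit the criterion can be met, but only if almost every Maintenance day is a seizure day:
- 33/42 is 22.0 per 28. Exceeding +25% needs more than 27.5 per 28, which is 83 of 84 days.
- 32/42 is 21.33. Exceeding +30% needs more than 27.73, which is 84 of 84 days.
- 27/42 is 18.0. Exceeding +50% needs more than 27.0, which is 82 of 84 days.

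Well below the limits there is ample room: the maximum increase is +180% at b = 10 and +100% at b = 14. It falls to +40% at b = 20, +27.3% at b = 22 and 0% at b = 28. The two problems interact: a child at b = 22 can meet the cut-off in 2.2.2.2 but not either one in 9.2.

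**Days against counts (illustrative values, not from the documents).** A child who goes from 5 to 10 seizures every day moves from 140 to 280 seizures per 28 days, or +100%. On seizure days the same child moves from 28 to 28, or 0%. The reverse change is −50% on counts, which would meet the responder criterion, and again 0% on days.

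**The case against.** The strongest reply is that these are exploratory variables in an uncontrolled, descriptive study of about 50 children. No decision rule is tied to any cut-off, and percent change by syndrome is summarised anyway. Seizure days are also the protocol's primary and efficacy metric, and counts are less reliable when seizures cluster. All of this stands. It lowers the severity and argues for keeping days as the main metric. It does not settle which cut-off applies.

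A reader might infer that children with frequent seizures can never be counted as worsened. The documents do not support that. The block depends on the number of days with seizures, not the number of seizures. A child with many seizures on 10 Baseline days per 28 can still show up to +180%. Entry requires only 2 or more events in 6 weeks (Protocol 6.1), and no Baseline distribution is given, so many children may be far from the limit.

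A reader might also infer that a syndrome with daily seizures would look free of exacerbation in the study as a whole. That goes too far. A clinically significant rise in seizure frequency or intensity is recordable as an adverse event (Protocol 11.1.1). Treatment-emergent events, disposition with reasons, and hospital and emergency room use are all repeated by syndrome (SAP 8.2.2, 5.1 and 9.1.5). These are partial safeguards. Adverse event recording depends on the investigator's judgement. The EEG increase table (SAP 8.1.1) and the Global Impression summaries (SAP 9.1.2 and 9.1.3) are not specified by syndrome.

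Finally, the SAP does not state outright that the worsening proportions use days. That is inferred from the only derivation supplied. If counts were intended, the ceiling disappears and the defect becomes a missing derivation.

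**Conclusion.** The contradiction in cut-offs is certain: the variable in Section 2.2.2.2 has no planned analysis, and the cut-offs in Section 9.2 match no listed worsening variable. The metric is unnamed.

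The ceiling is exact arithmetic, conditional on seizure days being the metric. It confines the problem to this one set of proportions and to children at or above the limits shown in the working. How many children that is cannot be determined from the documents. Within that group, no diary-based summary by syndrome can register more seizures per day, because every planned diary summary uses seizure days.

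This is a should-fix point. It bears on a stated purpose of the study, but it leaves the choice of primary variable unaffected.

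**What to change.** 1. Use the same cut-offs in SAP Sections 2.2.2.2 and 9.2. Tabulating more than 25%, 30% and 50% would cover both.
2. State that the responder and worsening proportions are based on seizure days per 28 days. Beside the worsening table, report by syndrome how many subjects have a Baseline at or above the limit for each cut-off (22.4, 21.54 and 18.67 days per 28).
3. Add a supplementary table of the same proportions based on diary seizure counts: total generalized seizures × 28/D. Keep seizure days as the main metric.

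The cost is SAP wording, one derived variable and one extra table, from data the protocol says the diary collects. The diary form is not in the documents, so the sponsor should first confirm that it yields daily counts. The downside is small: counts of clustered absence or myoclonic seizures are less accurate, so the count table needs a stated rule for clusters and should remain supplementary.

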## **10 PHARMACOKINETICS**

### **10.1 Descriptive statistics of LCM and AED plasma concentrations**

The results of LCM plasma concentrations will be described by the method of descriptive statistics: n,  $\geq$  limit of quantification (LOQ), arithmetic mean, SD, median, geometric mean, and geometric CV. Summary statistics will only be calculated if at least 2/3 of the data are above the lower LOQ. Values  $<$ LOQ will be set to LOQ/2 for the determination of summary statistics.

The summary of LCM plasma concentrations will be presented by dose level during the Maintenance Period (dose with the longest duration during the Maintenance Period) and visit. The dose levels will be combined as 4-6 mg/kg/day, 7-8 mg/kg/day, 9-10 mg/kg/day, and 11-12 mg/kg/day.

Other AED plasma concentrations will only be listed.

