^m For subjects aged 5 to 17 years.ⁿ For female subjects of childbearing potential, a serum pregnancy test will be performed at Visit 1, Visit 9 or the ET Visit, and the End of Taper Visit. A serum pregnancy test will also be performed at the Safety Follow-Up Visit only if blood is collected for other laboratory tests. If no blood is collected for other assessments, then a urine pregnancy test will be performed. A urine pregnancy test will be performed at all other visits, as scheduled in Table 5-1.^o The Tanner Stage will be performed only for subjects who are pubescent at Visit 1 or who will enter puberty during the course of the study.^p Blood samples for analysis of concomitant AED plasma concentrations and LCM plasma concentration will be drawn along with clinical chemistry and hematology samples; predose at Visit 2 and postdose at Visit 9 or the ET Visit.^q The C-SSRS will be completed for all subjects ≥6 years of age.^r If the Unscheduled Visit is due to an AE, then the C-SSRS is required.^s The Achenbach CBCL: CBCL/1½-5 for pediatric subjects from 18 months to 5 years 11 months and CBCL/6-18 for pediatric subjects aged 6 years and older; to be completed by the parent(s)/legal representative(s) (estimated completion time 45 minutes). For each subject, the same version of the scale that was completed at Visit 2 (CBCL/1½-5 or CBCL/6-18) should be maintained for the duration of the study and should be completed by the same parent/legal representative. The same scale should be completed again by the same parent(s)/legal representative(s) later in the open-label study, SP848 (if applicable). The Achenbach CBCL will be used only in countries where a translated version is available.^t Bayley Scales of Infant and Toddler Development®, Third Edition for pediatric subjects <18 months of age at Baseline enrolled in English-speaking countries.^u The BRIEF-P should be used for subjects who are ≥2 years to <5 years of age at Visit 2, and the BRIEF should be used for subjects who are ≥5 years of age at Visit 2. The same version of the scale that was completed at Visit 2 (BRIEF-P or BRIEF) should be maintained for each subject for the duration of the study. The BRIEF-P and BRIEF will be used only in countries where a translated version is available.^v The version of the PedsQL used at Visit 2 should be consistent with the subject's age at Visit 2 and should be maintained for each subject for the duration of

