13.4.2 Pharmacokinetic analyses

A listing of LCM and AED plasma concentrations will be presented. A statistical analysis of the effect of LCM on AED concentrations will be performed.

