### **2.2.3 Pharmacokinetic and pharmacodynamic variables**

Plasma concentrations of LCM and concomitant AEDs will be obtained in order to:

- Develop a population PK model of LCM
- Investigate the effect of LCM on the steady-state plasma concentrations of concomitant AEDs
- Investigate the correlation between LCM plasma concentrations and efficacy or safety

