### **3.9 Changes to protocol-defined analyses**

Not applicable.

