### **10.2 Population pharmacokinetics and exposure response**

Population pharmacokinetics and exposure-response modeling are not in the scope of the SAP and will be described in separate data analysis plans.

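### SAP 10.1 replaces the protocol's analysis of lacosamide's effect on concomitant AED levels with a listing, undeclared in SAP 3.9, and its LCM dose bands have no rule for subjects of 50 kg or more

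*SAP*

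**What the plan says.** **AED concentrations.** Protocol 13.4.2 has two sentences. The first promises a listing of LCM and AED concentrations. The second adds: "A statistical analysis of the effect of LCM on AED concentrations will be performed". SAP 2.2.3 repeats the purpose stated in Protocol 4.3: "Investigate the effect of LCM on the steady-state plasma concentrations of concomitant AEDs". SAP 10.1 then summarises LCM only and says of the rest: "Other AED plasma concentrations will only be listed". SAP Amendment 1 (section 14.1, Change #7) records that other AEDs were previously to be summarised as well. SAP 10.2 assigns some work elsewhere: "Population pharmacokinetics and exposure-response modeling are not in the scope of the SAP and will be described in separate data analysis plans". Under the heading "Changes to protocol-defined analyses", SAP 3.9 states that nothing applies.

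Protocol Table 5-1 schedules both the LCM and the AED samples "predose at Visit 2 and postdose at Visit 9 or the ET Visit". Protocol 10 requires the times of the last LCM and AED doses and of the blood draw to be recorded. Protocol 7.8.1 requires AED doses to stay stable to the end of Maintenance.

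**LCM bands.** For the LCM summary, SAP 10.1 says: "The dose levels will be combined as 4-6 mg/kg/day, 7-8 mg/kg/day, 9-10 mg/kg/day, and 11-12 mg/kg/day". Protocol 5.4 doses heavier subjects in mg/day: "Subjects ≥50kg: LCM 200 to 600mg/day (tablets/oral solution". SAP 10.1 gives no conversion, rounding rule or mg/day band for them. The only conversion in the SAP is in 8.4, where the mean daily dose of tablet users is divided by baseline weight for the exposure summary.

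**The concern.** A listing satisfies the first sentence of Protocol 13.4.2 but not the second. The SAP therefore keeps an aim without an analysis and states that it has made no change to the protocol's analyses. Someone who checks only 3.9 would not learn that an analysis had been dropped.

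The AED dose is held fixed by design, but AED exposure is not. The paired concentrations are the direct check on whether exposure moved after LCM was added, and a by-subject listing over several AEDs does not answer that in a usable form.

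The bands matter because this is the only table of LCM concentration by dose that the SAP describes. If a programmer has to invent the rule that places heavier subjects, some may be left out of the table or placed arbitrarily.

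**Working it through.** The plan gives no power, alpha or precision figure on this point, so there is none to reproduce.

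**1. Commitment against plan**

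| Place | AED concentrations |
|---|---|
| Protocol 4.3 | effect of LCM is a stated purpose |
| Protocol 13.4.2 | listing, plus a statistical analysis of the effect |
| SAP 2.2.3 | same purpose repeated |
| SAP 10.1 | listing only |
| SAP 10.2 | other plans named for population PK and exposure-response only |
| SAP 3.9 | no change declared |

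The analysis appears in the protocol, in no analysis section of the SAP, and in no other plan that the documents name.

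**2. What a ratio could show**

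Assumptions, not in the documents: the within-subject CV and the number of subjects per AED. About 50 subjects take 1 to 3 AEDs each (Protocol 5.1.2 and 6.1), so counts per drug may be small.

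- SD on the log scale: s = √ln(1 + CV²). At CV 30%, s = √ln(1.09) = 0.294.
- 90% half-width of the log ratio: t(0.95, n−1) × √2 × s / √n.
- n = 15: 1.761 × 1.414 × 0.294 / √15 = 0.189; exp(±0.189) = 0.83 and 1.21.
- n = 5: 2.132 × 1.414 × 0.294 / √5 = 0.396; exp(±0.396) = 0.67 and 1.49.

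| Assumed CV | n = 5 | n = 15 |
|---|---|---|
| 20% (s = 0.198) | ×0.77 to ×1.31 | ×0.88 to ×1.14 |
| 30% (s = 0.294) | ×0.67 to ×1.49 | ×0.83 to ×1.21 |
| 50% (s = 0.472) | ×0.53 to ×1.89 | ×0.74 to ×1.36 |

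**3. Do the bands hold the permitted doses?**

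*Below 50 kg.* Every whole-number dose from 4 to 12 mg/kg/day falls in a band.

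*50 kg and above.* mg/kg/day = (mg/day) / kg. Protocol 7.2 allows 50 mg steps, so there are nine doses from 200 to 600.

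- 50 kg: all nine fit (4, 5, …, 12).
- 60 kg: 200 → 3.33, 400 → 6.67 and 500 → 8.33 fit no band (3 of 9).
- 80 kg: 200 → 2.50, 250 → 3.13, 300 → 3.75, 500 → 6.25 and 550 → 6.88 fit no band (5 of 9).
- 200 mg/day is below 4 mg/kg/day above 200/4 = 50 kg. It rounds to less than 4 above 200/3.5 = 57.1 kg.

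*Share of pairs.* The documents give no weight distribution. Assume every whole kilogram from 50 to 80 (31 weights) and every dose equally likely.

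| | 50 mg steps (279 pairs) | 100 mg steps (155 pairs) |
|---|---|---|
| in no band, literal limits | 128 = 45.9% | 73 = 47.1% |
| of these, below 4 mg/kg/day | 53 = 19.0% | 35 = 22.6% |
| in no band after rounding to whole mg/kg | 32 = 11.5% | 23 = 14.8% |

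Rounding closes the gaps between bands. What remains lies below the lowest band.

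**The case against.** **The change is disclosed.** SAP Amendment 1 says openly that AED concentrations are now only listed. A reader might infer from 3.9 that the downgrade was concealed, but the amendment log rules that out. It does not repair 3.9, where departures from the protocol belong, and its general rationale gives no reason for this item.

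**Another plan may cover it.** One might infer that no plan does. The documents do not show that either, because the separate plans are not available and SAP 2.2.3 lists the AED effect beside the population PK model. What stands is that the documents name no plan for it.

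**Little depends on it.** A reader might infer that without the analysis, seizure and AE changes can no longer be attributed to LCM. That goes too far: the study is open-label with no control arm, so firm attribution is not available whatever the AED levels show. PK is an additional objective, and AED levels enter no primary or secondary variable.

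**A ratio could be uninformative.** The Visit 9 sample may be drawn at any time after dosing, so a single-sample ratio can mix peak and trough, and small groups give wide intervals. This is a sound reason to label the result descriptive. It is not a reason to leave it out without saying so.

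**The bands follow a whole-number convention.** The upper three match Protocol Table 7-4, and the listings keep all data. One might infer from the 46-47% that nearly half of the heavier subjects would be lost. That share is of a uniform grid under literal limits, not of trial subjects, and rounding cuts it to 11-15%. The rounding rule is not written down, however, and rounding does not help 200 mg/day above about 57 kg.

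**Conclusion.** The main point holds on the text alone: an analysis committed to in Protocol 13.4.2 is reduced to a listing in SAP 10.1, no other named plan covers it, and SAP 3.9 is wrong to declare nothing. The precision figures rest on assumed CVs and group sizes. At 30% CV, 15 subjects on one AED could show a moderate shift, while 5 could only describe one.

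The secondary point also holds, but is smaller. The LCM bands need a rule for mg/day doses and a place for 200 mg/day. The shares of 46-47% (literal) and 11-15% (rounded) depend on a uniform 50-80 kg grid and do not forecast the trial population.

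Severity: should-fix. The study is exploratory and no primary result depends on either point.

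**What to change.** **AED analysis (SAP 10.1).** For each AED with enough paired samples, for example at least 5 subjects, report the within-subject Visit 9/Visit 2 geometric mean ratio with a 90% CI. Restrict it to subjects whose AED dose was unchanged. Show the time since the last AED dose at each sample, and label the result descriptive because sampling times are not matched. If the sponsor prefers not to do this, record the omission and the reason in 3.9. If another plan covers it, name that plan in 10.2.

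**LCM bands (summary table only; no dosing change).**
- Below 50 kg: contiguous bands, for example 4 to <7, 7 to <9, 9 to <11 and 11 to 12 mg/kg/day.
- 50 kg and above: mg/day groups based on Protocol Table 7-5 that cover the permitted range: 200, 250-300, 350-400, 450-500 and 550-600, with the lowest two merged if sparse. Table 7-5 itself has rows for 150-200 and 250-300. State where an intermediate oral-solution dose would go.

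**Cost.** SAP wording, one added table and a regrouped one. No new visits or samples are needed: both blood draws and the recording of dose and sampling times are already in the protocol.
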